7.6.3	Ophthalmic examinations	24
8.	Special Statistical/Analytical Issues	25
8.1	Interim Analysis	25
8.2	Changes in the Planned Analysis	26
A.	APPENDICES	28
	List of Tables	28
	List of Figures	30
	List of Listings	31

List of Abbreviations and Key Terms

α	Type I error
ADE	Adverse Device Effect
AE	Adverse Event
ASIC	Application specific integrated circuit
ATC	Anatomical Therapeutic Chemical Classification
β	Type II error
CIP	Clinical Investigation Plan
DSMB	Data Safety Monitoring Board
FAS	Full-analysis-set
GAT	Goldmann Applanation Tonometry
HLT	High level term
HLGT	High level group term
IO	Intraocular
IOL	Intraocular lens
IOP	Intraocular Pressure
ITT	Intention to treat
LLT	Lowest level term
N	Sample number
OCT	Ophthalmic Coherence Tomography
p0	Proportion of patients in stage 1 with positive outcome
p1	Proportion of patients overall with positive outcome
POAG	Primary open angle glaucoma
PT	Preferred term
SADE	Serious Adverse Device Effect
SAE	Serious Adverse Event
SAP	Statistical Analysis Plan
SES	Safety evaluation set
SOC	System organ class
V	Visit

1. Introduction

This Statistical Analysis Plan (SAP) contains a more technical and detailed elaboration of the principal features of the statistical analyses described in the Clinical Investigation Plan Rev. G, date 05th January 2016, and includes planned detailed procedures for executing the statistical analysis of the primary and secondary variables and other data. The SAP is finalised and signed prior to hard lock of the database.

2. Study Design and Objectives

2.1 Study Design

The trial will be conducted as an open, prospective, multicenter single-arm clinical trial following the principle of the two-stage design described by Simon (Simon, 1989) in patients with Primary Open Angles Glaucoma (POAG) and indicated cataract surgery. The purpose is to evaluate the safety of the ARGOS-IO system and to compare its performance to the Goldmann Applanation Tonometry (GAT).

All 22 patients will be enrolled consecutively, until a serious adverse device effect (SADE) occurs. In that case, the DSMB will be called, and decides whether the enrollment can be continued or not.

An interim analysis will be performed after half of the study population (11-14 subjects) is enrolled with a minimum follow-up of 1 month. Another interim analysis to assess Safety and Performance will be performed, when all patients have completed the 3 month follow-up visit, the 6 month follow-up visit and every time an SADE occurs.

In order to take the two-stage design described by Simon into account, the trial will be terminated, if more than 1 patient out of the first 11 patients enrolled experiences SADEs during the first 3 months of the post-surgical follow-up period.

A conclusion for safety will be made at the 5% significance level, if two or fewer of the total 22 patients experience an SADE. A corresponding 95% confidence interval for the SADE rate will be calculated according to the procedure of Koyoma (2008).

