6.2 Risk Management Process

Potential risks related to the intended use and foreseeable misuse of the ARGOS-IO system are identified and mitigated on an ongoing basis according to the risk management analysis prescribed by ISO 14971:2012 in combination with ISO/TR 24971: 2013 and detailed in the document ARGOS-IO Implant: Risk Management Report (01-RE-00D). The analysis is updated at least once annually, including the specific time points: before the start of the clinical investigation of the device, at the completion of the first phase of the study, at each interim analysis and whenever significant new information regarding the risk profile or AEs becomes available. Risks were identified based on a list of questions contained in Annex C of ISO 14971:2012, information and data obtained from published standards, scientific technical data, field data from similar devices already in use, clinical and preclinical evidence, results of appropriate investigations and expert opinion.

The sources listed above were also used to assign rankings for severity of possible harms and probability of occurrence for each identified risk. The rankings used are defined in Table 2 and Table 3, respectively.

Table 2. Levels of Severity used for Risk Assessment

Level of Severity	Possible Harm
1	No harm
2	Very brief, harmless discomfort
3	Short term discomfort
4	Minor damage or disablement, no expert medical intervention required
5	Minor damage or disablement, that may require expert medical intervention
6	Slight damage or disablement that requires expert medical intervention
7	Temporary damage or marked disablement that requires expert medical intervention
8	Permanent damage or disablement without further disease
9	In combination with the diseases potentially lethal damage or disablement
10	Patient death

Source: ([name], 2014)

Table 3. Levels of Probability used for Risk Assessment of ARGOS-IO system

Level of Probability	Frequency of Occurrence
1	Improbable
2	1 in 10 ⁵ uses
3	1 in 5x10 ⁴ uses
4	1 in 10 ⁴ uses
5	1 in 5x10 ³ uses
6	1 in 10 ³ uses
7	1 in 5x10 ² uses
8	1 in 10 ² uses
9	1 in 10 uses
10	Every use

Source: ([name], 2014)

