A dichotomy was seen in severity of risks, with all risks having a severity higher than 7 related to the implant itself or the surgical procedure and those having a severity of 7 or less related to IOP measurements. On the basis of both severity and probability, the identified risks were categorized as either acceptable, as low as reasonably possible given the available risk mitigation measures or unacceptable. The rankings used are shown in Table 4.

Table 4. Risk Acceptability Matrix

		Severity									
		1	2	3	4	5	6	7	8	9	10
Probability	1	y	y	y	y	y	y	y	y	n	n
	2	y	y	y	y	y	y	y	y	n	n
	3	y	y	y	y	y	y	y	y	n	n
	4	y	y	y	y	y	y	y	a	n	n
	5	y	y	y	y	y	y	a	n	n	n
	6	y	y	y	y	y	y	n	n	n	n
	7	y	y	y	y	y	y	n	n	n	n
	8	y	y	y	y	y	a	n	n	n	n
	9	y	y	y	y	y	n	n	n	n	n
	10	y	y	y	y	a	n	n	n	n	n

Source: ([name], 2014)

Risk control measures were undertaken to reduce the probability of unacceptable and borderline acceptable risks. Where ever possible, priority was given to mitigating the risk first through design changes to eliminate it and if this was not feasible, by integrating protective measures in the medical device itself or in the manufacturing process to minimize the risk. Risks due to human factors that could not be eliminated or checked in advance, such as mistakes in the implant or explant procedures will be mitigated by including clear warnings and cautions in the literature and packaging accompanying the device and by limiting implantation use to experience ophthalmic surgeons. Finally, the resulting measures were reassessed to ensure that no new risks had been introduced during the mitigation process.

 Impladata Ophthalmic Products GmbH	Clinical Investigation Plan ARGOS-02	Revision C
		Page 49 of 106

6.3 Anticipated Adverse Device Effects associated with the ARGOS-IO sensor device and their control

Anticipated potential risks of a long-term implantation of the ARGOS-IO pressure sensor are associated with:

- Surgical implantation of the ARGOS-IO pressure sensor
- Possible side effects and/or tolerance in the early or deferred post-operative period
- Possible crowding of ocular structures due to presence of the implant
- Side effects of the wireless IOP measurement
- Incompatibility with other surgical procedures or medical devices, such as silicone oil tamponade, glaucoma drainage device (GDD) and cochlear implants
- Incompatibility of interactions of the ARGOS-IO implant with topically applied ophthalmic medications and vice versa

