The trial will be conducted as an open, prospective, multicenter single-arm clinical trial using the two- stage design described by Simon (Simon, 1989). In the first stage, 11 patients will have an ARGOS-IO pressure sensor implanted, after which enrollment will be halted until the patients have completed their 3 months follow-up visits and an interim analysis has been performed. The interim analysis will be reviewed by the DSMB. If two or more of these 11 patients in the first stage are found to have had an SADE, further enrollment into the study will be stopped. If not, enrollment will resume until another 11 patients have had an ARGOS-IO pressure sensor implanted. If two or fewer of the total 22 patients experience an SADE, a conclusion for safety will made at the 5% significance level. A corresponding 95% confidence interval for the SADE rate will be calculated according to the procedure of Koyoma (2008).

All patients who receive an ARGOS-IO implant will return for 10 follow-up visits to the clinic (day 1, 3, 10, 30, 60, 90, 120, 180, 240, 360) during the 12-month post-surgical period (see Table 6: Assessment Schedule). To allow comparison of the IOP measurement methods, IOP measurements will be made at every visit with GAT and with the ARGOS-IO systems beginning at V5 (day 30).

Ammended

The trial will be conducted as an open, prospective, multicenter single-arm clinical trial. All 22 patients will be enrolled consecutively, until a SADE occurs. In that case, the DSMB will be called, and decides whether the enrollment can be continued or not. If two or fewer of the total 22 patients experience an SADE, a conclusion for safety will made at the 5% significance level. A corresponding 95% confidence interval for the SADE rate will be calculated according to the procedure of Koyoma (2008).

All patients who receive an ARGOS-IO implant will return for 10 follow-up visits to the clinic (day 1, 3, 10, 30, 60, 90, 120, 180, 240, 360) during the 12-month post-surgical period (see Table 6: Assessment Schedule). To allow comparison of the IOP measurement methods, IOP measurements will be made at every visit with GAT and with the ARGOS-IO systems beginning at V5 (day 30).

Page 66, 8.3.3.1 Study stopping rules:

RevC

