2.5 Study Hypothesis

The specific hypothesis to be tested in this single arm two-stage design study is that the SADE rate is lower than 25%. It is expected that the observed SADE rate will be at most 6%. More precisely, let p be the true proportion of subjects with no SADEs, p_0 the proportion of subjects no SADE to be rejected and p_1 the expected proportion of patients overall without SADE. Then, the null hypothesis H_0 and the alternative hypothesis H_1 are:

$$H_0 = p \leq p_0 = 0.25 \quad \text{vs.} \quad H_1 = p > p_1 = 0.25.$$

If at most 2 SADE's occur in the 22 patients enrolled, a SADE rate lower than 25% can be concluded. This will be illustrated by the 95% confidence interval for the SADE rate which will be calculated using the method proposed by Koyama (Koyama & Chen, 2008). If the obtained

confidence interval does not include any value lower than 0.94, it can be concluded that the SADE rate is at most 6%.

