2.9 Sample Size Calculation

The primary aim of this study is to show “safety”, which will be evaluated based on the percentage of subjects who experience an SADE (= “non-safety), as defined in the primary endpoints.. To minimize the required sample size and consequently the number of patients exposed to risk while at the same time maximizing the chances of detecting safety events, the sample size calculation follows the principle of a two-stage design as proposed by Simon (Simon, 1989). The event of interest was defined as patients with at least one serious device related adverse event (SADE) in the 3 month period immediately following implantation. Based on a probability of non-events of $p_0=0.75$ for the first stage and an overall acceptable probability of $p_1=0.94$, a sample size of at least 11 evaluable patients in the first stage and additional 11 patients in the second stage are required. This maintains a type 1 error probability of 5% and the power of 80% based on minimizing the maximal sample size. Table 2 summarizes the consequences of the sample size calculation on the study design.

Table 2: Two-stage study design

	First Stage	Overall
SADE-free Patients		
Proportion	$p_0 = 0.75$	$p_1 = 0.94$
Minimum number required	10	20
Patients with SADE		
Proportion	$1 - p_0 = 0.25$	$1 - p_1 = 0.06$
Maximum number allowed	1	2
Total Number of Patients	11	22

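### The 5% error level supports only a 3-month SADE rate below 25%, yet the plan reports a pass as a conclusion for safety, and CIP 7.2 as a rate of at most 6%

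*SAP*

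**What the plan says.** The same count leads to differently worded conclusions in different places.

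- SAP 2.1: "A conclusion for safety will be made at the 5% significance level, if two or fewer of the total 22 patients experience an SADE".
- Protocol addendum, amended CIP 8.1.1: "If two or fewer of the total 22 patients experience an SADE, a conclusion for safety will made at the 5% significance level". The amended synopsis draws the same conclusion from the same count, without the significance level.
- SAP 2.5: "The specific hypothesis to be tested in this single arm two-stage design study is that the SADE rate is lower than 25" per cent. It adds that at most 2 SADEs in 22 patients permit that conclusion, describes 6% as the rate expected, and makes a claim of at most 6% depend on the confidence interval.
- CIP 7.2, which the addendum as supplied does not change, gives the hypothesis under test as a SADE rate of at most 6%.
- SAP 7.2 and amended CIP 9.1 speak of a decision on, or for, safety.
- SAP 2.9 introduces the design values with "for the first stage and an overall acceptable probability of" p1 = 0.94, and says of the 11 + 11 design: "This maintains a type 1 error probability of 5% and the power of 80% based on minimizing the maximal sample size".

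Two further success criteria differ from 2 of 22. CIP 9.5 requires fewer than two SADE patients in 22. The amended synopsis and amended 9.2 declare success if the final event rate is below 6%.

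**The concern.** A reader who meets a conclusion for safety at the 5% level will assume that a device that is not safe passes at most 5% of the time. That holds only if not safe means a SADE rate of 25% or more. A reader who starts from CIP 7.2 will take a pass as evidence that the rate is at most 6%. In the design, however, 6% is the value at which power was set, not the value tested against. The documents give no reason for choosing either 25% or 6%.

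What is at stake is how the primary result may be reported. The test is unaffected, but the sentence drawn from a pass could claim much more than 22 patients can show.

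**Working it through.** **Inputs.** From SAP 2.9: p0 = 0.75 and p1 = 0.94 SADE-free, i.e. SADE rates of 25% and 6%; 11 patients in stage 1 and 22 overall. From SAP 2.1: terminate if more than 1 of the first 11 has a SADE; pass if 2 or fewer of 22 do. Amended CIP 8.1.1 and 9.1 keep 2 of 22 but drop the stage 1 rule, so both versions are computed.

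**Formulas**, with q the true SADE rate:

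- With the stage 1 stop: P(pass) = P(X1=0)·P(X2≤2) + P(X1=1)·P(X2≤1), where X1 and X2 are independent Bin(11, q).
- Without it: P(pass) = P(X≤2), where X is Bin(22, q).

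**Reproducing the plan's figures**

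- q = 0.25: 0.04224 × 0.45520 + 0.15486 × 0.19710 = 0.0192 + 0.0305 = 0.0497. The stated 5% is met.
- q = 0.06: 0.50630 × 0.97524 + 0.35549 × 0.86178 = 0.4938 + 0.3064 = 0.800. The stated 80% power is met.
- Expected sample size at 25%: the chance of continuing is 0.04224 + 0.15486 = 0.197, so 11 + 11 × 0.197 = 13.2, as given in CIP 9.2 (Revision C).

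The design is computed correctly for 25% against 6%.

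**Between the two design points**

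- q = 0.10, with the stop: 0.31381 × 0.91044 + 0.38355 × 0.69736 = 0.2857 + 0.2675 = 0.553.
- q = 0.10, without it: 0.0985 + 0.2407 + 0.2808 = 0.620.

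| True SADE rate | Pass, with stage 1 stop | Pass, 2 of 22 alone |
|---|---|---|
| 25% | 5.0% | 6.1% |
| 15% | 29.0% | 33.8% |
| 10% | 55.3% | 62.0% |
| 6% | 80.0% | 85.8% |

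Read without a stage 1 stop, the amended rule slightly exceeds 5% even at 25%.

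**Can a pass show at most 6%?** The plan specifies the Koyama and Chen interval. As an illustration, the ordinary exact two-sided 95% interval for 2 of 22 is 1.1% to 29.2%. For 0 of 22 the upper limit is 1 − 0.025^(1/22) = 15.4%. On that interval no passing count, including zero, excludes rates above 6%.

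**The competing criteria.** 2/22 = 9.1%, which is not below 6%; 1/22 = 4.5%, which is. Taken as an observed rate, the 6% criterion therefore amounts to at most 1 of 22, as in CIP 9.5. That rule passes 33.9% of the time at a true rate of 10%. A result of exactly 2 of 22 succeeds under SAP 2.1 and fails under CIP 9.5 and the below-6% wording.

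**The case against.** The strongest reply is that the SAP already discloses the narrower claim. SAP 2.5 says what at most 2 SADEs allow one to conclude, calls 6% expected, and requires the confidence interval before any 6% claim; SAP 7.2 repeats that condition, and SAP 2.9 tabulates both proportions. A careful reader can therefore recover the right interpretation. Every SADE also triggers DSMB review and may end enrolment, which can only lower the pass probabilities above. All of this stands, and it is why the point is minor. It does not remove the looser wording in SAP 2.1 and amended CIP 8.1.1, or the different hypothesis in CIP 7.2.

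A reader might go further and use the risk tables in CIP 6.2 (Tables 2 to 4) as the sponsor's limit for an acceptable SADE rate. Table 4 marks severity 6 and above as not acceptable at 1 in 10 uses, so the 55% to 62% at a true rate of 10% could be read as how often an unacceptable device is declared safe. The documents do not support this:

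- Nothing links the endpoint to those tables. They rate hazards one by one ("On the basis of both severity and probability, the identified risks were categorized as either acceptable, as low as reasonably possible"), by frequency per use. The endpoint is a per-patient, 3-month composite that counts events with only a possible device relation.
- Placing every SADE at severity 6 or above is an inference. One that qualifies by hospitalization alone could be argued to be level 5, which is acceptable at 1 in 10.
- Reading the matrix hazard by hazard changes the answer. Ten hazards of 1% each at severity 6 fall in the intermediate category, not the unacceptable one.
- The 55% to 62% holds at exactly 10%. At 15% the rule passes 29% to 34% of the time, and at 25% it passes 5% to 6%.

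Nor does the risk/benefit assessment in CIP 6.7 rest on passing this rule. It is made before the trial, from the risk management process.

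**Conclusion.** The concern holds as one of wording. The 5% error level applies to the claim that the 3-month SADE rate is below 25%, and to nothing stronger. A pass does not show a rate of at most 6%, and it does not show safety in general: at a true rate of 10% the rule passes 55% of the time with the stage 1 stop and 62% without it. It does not follow that the plan accepts a risk it elsewhere rejects, because the documents set no acceptable SADE rate against which to make that claim.

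The figures assume independent patients with a common SADE rate, 22 evaluable patients, and no discretionary DSMB stop. The SAP refers to CIP Rev. G; the protocol text available is Revision C with an addendum, so the current wording of CIP 7.2 and 9.5 should be checked first. Severity: minor.

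**What to change.** 1. In SAP 2.1, the amended CIP synopsis, amended CIP 8.1.1 and CIP 7.2, state the conclusion as: the 3-month SADE rate is below 25%. Align the decision wording in SAP 7.2 and amended CIP 9.1 with it.
2. In SAP 2.9, describe p1 = 0.94 as the expected proportion, as SAP 2.5 does, not as an acceptable one.
3. Beside the rule, give its pass probabilities at true SADE rates of 6%, 10% and 25%, and say whether the stage 1 stop is assumed.
4. Reconcile 2 or fewer of 22 with the fewer-than-two criterion in CIP 9.5 and the below-6% criterion in the amended synopsis and 9.2, so that one success criterion remains.

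The cost is a few sentences in the SAP and CIP and a less favourable headline claim. No patients, procedures, sample size or critical values change under items 1 to 3. Item 4 leaves the SAP rule as it is if 2 of 22 is confirmed.

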2.2 Treatments

2.2.1 Investigational Device

The ARGOS-IO system was developed for the wireless, contactless measurement of the hydrostatic pressure of the aqueous humor (intraocular pressure (IOP)) in patients with diagnosed glaucoma, or elevated or instable IOP that places them at a risk of ocular damage and loss of visual acuity. It enables numerous IOP measurements daily, providing a complete IOP profile for the entire interval between office visits, and allowing timely detection of both peaks due to patient activities and circadian rhythms and trends due to disease progression.

It is made up of four components:

- the ARGOS-IO implant, which is introduced into the area between the intraocular lens and the iris (ciliary sulcus) using standard procedures that employ an implant injector similar to those commonly used to insert intraocular lenses (IOLs),
- the external hand-held Mesograph reading device, which in the near vicinity of the eye establishes an inductive current between it and the micro-coil, thereby supplying the Application Specific Integrated Circuit (ASIC) with power and permitting data transmission,
- the implant injector and
- the Multiline Connector, which uploads the data recorded by the reader to a secure dedicated data base that can be accessed remotely by the Investigator.

2.2.2 Comparator

The ARGOS-IO system will be directly compared to the non-invasive Goldmann Applanation tonometry (GAT). Therefore, patients will not be exposed to any other active implantable comparators. GAT is the standard tonometry method to which all other tonometers have traditionally been compared.

No other investigational medical devices or medications will be used specifically for this clinical investigation, except for standard of care during surgery, standard devices for ophthalmic diagnostics, surgery follow up or Glaucoma treatment.

2.3 Trial Schedule

The estimated total duration of the study from first patient screened to last patient last visit is 21 months. The maximum duration of each patient's participation in this clinical intervention is 13

months. The point of enrolment is considered to be the time point at which potentially eligible patients sign the informed consent form. Surgery will be performed within 28 days of this time point. The patient will be followed-up for 12 months post-surgery to obtain data on safety and performance. All patients who receive an ARGOS-IO implant will return for 10 follow-up visits (V02 - V11) to the clinic (day 1, 3, 10, 30, 60, 90, 120, 180, 240, 360) during the 12-month post-surgical period. Table 1 shows the assessment schedule.

Table 1: Assessment Schedule

Visit	SC	V01	V02	V03	V04	V05	V06	V07	V08	V09	V10	V11
Indicative Days (D)	Up to 28 days before surgery	D0	D1	D3	D10 +/- 1 Day	D30 +/- 5 Days	D60 +/- 5 Days	D90 +/- 10 Days	D120 +/- 10 Days	D180 +/- 10 Days	D240 +/- 10 Days	D360 +/- 10 Days
GENERAL												
Informed consent signed	X											
Allocation of patient number	X											
Inclusion & exclusion criteria	X	X ¹										
Demography	X											
Past and current significant medical history	X											
Pregnancy test (urine beta-hCG)	X	X ²										
Optical Biometry (IOL Master)	X ³											
Cataract surgery and ARGOS-IO pressure sensor implantation		X										
Visual acuity (ETDRS) ⁴	X		X	X	X	X	X	X	X	X	X	X
Perimetry ⁵	X							X		X		X
External eye photography ⁶	X	X	X	X	X	X	X	X	X	X	X	X
User acceptance questionnaire (patient)												X
Implantation procedure questionnaire (surgeon)		X										
Concomitant medication	X	X	X	X	X	X	X	X	X	X	X	X
AE/ADE/SAE/SADE		X	X	X	X	X	X	X	X	X	X	X
Device malfunction		X	X	X	X	X	X	X	X	X	X	X
ANTERIOR SEGMENT												
Slit-lamp biomicroscopy ⁷	X		X	X	X	X	X	X	X	X	X	X
Ultrasound biomicroscopy (UBM)	X											
Optical coherence tomography (OCT) ⁸	X							X		X		X
Gonioscopy ⁹	X							X		X		X
Confocal Microscopy ¹⁰	X							X		X		X

Visit	SC	V01	V02	V03	V04	V05	V06	V07	V08	V09	V10	V11
Indicative Days (D)	Up to 28 days before surgery	D0	D1	D3	D10 +/- 1 Day	D30 +/- 5 Days	D60 +/- 5 Days	D90 +/- 10 Days	D120 +/- 10 Days	D180 +/- 10 Days	D240 +/- 10 Days	D360 +/- 10 Days
POSTERIOR SEGMENT												
Biomicroscopy ¹¹	X		X	X	X	X	X	X	X	X	X	X
Optical coherence tomography (OCT) ¹²	X							X		X		X
Fundus photography	X							X		X		X
IOP Measurement												
Goldmann Applanation tonometry ¹³	X		X	X	X	X	X	X	X	X	X	X
ARGOS-IO pressure sensor measurement ¹³						X ¹⁴	X	X ¹⁴	X	X ¹⁴	X	X ¹⁴
ARGOS-IO pressure sensor self-measurement ¹⁵						X	X	X	X	X	X	X

¹ Eligibility must be reassessed at V01 prior to surgery.

² For females of childbearing potential, a pregnancy test performed within 24 hours preceding surgery must be negative to confirm eligibility.

³ The Optical Biometry measurement using the IOL Master made at screening (SC) will be used to determine the implant sizes (IOL and ARGOS-IO implant).

⁴ The best corrected visual acuity will be determined after objective and subjective determination of refraction with the ETDRS chart in accordance with the EDTRS protocol.

⁵ Perimetry is performed to obtain an accurate examination of the peripheral extent of the visual field. Automated perimeters will be used either with standard glaucoma field, field 30-2 or equivalent.

⁶ External eye photography is performed through a slit lamp camera or equivalent. The outer eye shall be photographed in order to document potential changes to the iris or pupil structure.

⁷ Slit-lamp biomicroscopy is performed through an undilated pupil to assess the following anatomic parameters of the anterior segment: lids, conjunctiva, cornea, anterior chamber, iris, pupil, lens and anterior vitreous.

⁸ Anterior segment OCT is performed to evaluate effects on change in chamber angle after surgery and to assess the central corneal thickness.

⁹ Standard gonioscopy is used to confirm glaucoma classification and to determine predilation angle evaluation, the presence of iris tumors, foreign bodies, anterior synechiae and to predict the anterior chamber angle. The gonioscopic grading system according to Spaeth is used in this clinical investigation.

¹⁰ Standard confocal microscopy is used to determine the corneal endothelial cell density.

¹¹ Posterior segment biomicroscopy is performed through a dilated pupil using mydriatic agents by means of indirect ophthalmoscopy on a slit lamp with the aid of a 90D or "Superfield" or comparable lenses. This method is used to evaluate the following parameters: optic nerve lesions, other posterior pole lesions, vitreous opacities, optic nerve head, fundus lesions, retinal arteries and veins (AV), macular area, fundus periphery, normal and abnormal variations of the fundus.

¹² Posterior segment OCT is used to assess macular structures and the peripapillary nerve fiber layer.

¹³ IOP measurements will be made in series of 1 Goldmann Applanation tonometry (GAT) standard measurements followed by 3 ARGOS-IO system measurements, the first of which must occur within 10 minutes of the GAT. A series of measurements will be made at both the beginning and end of each visit. An interval of at least 60 minutes should lie between the last measurement of one series and the first measurement in the next.

¹⁴ At visits 5, 7, 9 and 11 at least 4 series of IOP measurements will be performed, with at least 60 minutes between the last measurement in one series and the first measurement in the next.

¹⁵ All patients will receive a MESOGRAPH reading device at Visit 05 in order to measure the IOP daily at home. Measurements shall be taken at least 4 times per day (morning, noon, afternoon, evening). The MESOGRAPH reading device will be connected to an external GSM module, which will transfer the measured value directly to a secure database. Investigators can log into the database in order to track the pressure levels of their patients as required.

